Laboratory chemistry ^{8b}		Х	X		X
Oligosaccharides in		Х	X		X
serum ^{7a}					

Clinical Protocol Number: CLI-LMZYMAA1-12

Clinical Protocol Version Number: 8.0

Date: 01 February 2019

Procedure	Registry Inclusion visit (approx 7 days)	Registry Baseline visit (Time 0)	Unscheduled Follow-up Routine Clinical Visits ¹	Six-month Follow-up Routine Clinical Visits ²	Yearly Follow-up Routine Clinical Visits
Serum Immunoglobulin class G, A, M ^{7a}		Х	X		X
Three-minute stair climbing test (3MSCT) ⁹ , when applicable		Х			X
Six-minute walk test (6MWT) ⁹ , when applicable		Х			X
Two-minutes walk test (2MWT) ¹⁰ , when applicable		X			X
Forced vital capacity (L and % of predicted)		Х	X		X
Electrocardiogram		Х	X		X
Hearing test (PTA)		Х	X		
Infections (including length and antibiotics requirement)		Х	X		X
Psychotic events		Х	X		X
Adverse Events /Adverse Drug Reactions ¹¹	X	Х	Х	Х	X
Health Assessment Questionnaires					
EQ-5D-5L		Х			X
Zarit Burden Interview		Х			X
CHAQ		Х			X
Behavior Checklists ¹²		Х			X

Abbreviations: ADA, anti-velmanase alfa-immunoglobulin G (IgG) antibody; CHAQ, Childhood Health Assessment Questionnaire; EQ-5D-5L, European Quality of Life Five Dimension Five Level Scale; L, litre; PTA, pure tone audiometry

1. Unscheduled follow-up visits can be performed at, but not limited to, three months after Lamzede treatment start, or whenever deemed appropriate according to treating physician's judgement for patients that start Lamzede treatment within one year prior to Registry inclusion.

2. Additional follow-up visit after six months is highly recommended for patients that start Lamzede treatment within one year prior to Registry inclusion.

- 3. If not taken or collected at Registry Inclusion visit.
- 4. Patients' retrospective data may be collected at the time of Registry enrolment if available. Baseline visits are recommended to be repeated for those patients who will start Lamzede therapy during the course of the study, before therapy is initiated.
- 5. Physical examination to collect vital signs, anthropometric measurements like height, weight, rate of growth and the ability to perform the endurance test at the study visit.
- 6. If applicable, information regarding weekly Lamzede therapy received by the patient need to be recorded within all the Registry duration

Clinical Protocol Number: CLI-LMZYMAA1-12	
Clinical Protocol Version Number: 8.0	Date: 01 February 2019

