Questionnaires will be managed through a paper process only. Two copies are foreseen to be available: the original form will be shipped to the CRO for entering the data in the study database and the second copy will be archived in the Investigator's Site File at the site. The original copy will then be collected in the main Trial Master.

After the completion of data collection and cleaning, a review meeting will be held to determine the occurrence of any protocol violation and to define the patient populations for the analysis. Once the database has been declared to be complete and accurate, it will be locked, and the planned statistical analysis will be performed.

If the database is unlocked after the initial lock, the process must be carefully controlled and documented; updates to the study data must be authorised by Chiesi.

At the study conclusion, a complete copy of the study data will be created for archival purposes at Chiesi. The investigators will receive copies of the patient data for retention at the investigational sites.

^a Local laboratory will be used in Germany as per local clinical practice. Central laboratory will be adopted in extra-German sites.

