9.7 Data Analysis

The following describes the statistical analysis as it is foreseen at the time of planning the trial. Detailed methodology for the summary and statistical analyses of data collected in this study will be documented in a Statistical Analysis Plan (SAP).

9.7.1 Populations for Analysis

The following analysis sets will be defined:

- The Lamzede Safety analysis set (L-SAF) will contain all enrolled patients fulfilling inclusion criteria who have, at some time, received Lamzede treatment. This will include all patients entering the study currently taking Lamzede and all patients not taking Lamzede on entry to the study, but who begin doing so during the study. The latter group (those not taking Lamzede on entry to the study, but who begin doing so during the study) will only be classed as in the L-SAF from the time that they begin taking Lamzede. As is common practice, patients who have taken any amount of Lamzede, even if only one dose, will be included in the safety analyses. With regards to L-SAF definition, a minimum individual follow up of 1 month after last dose taken will be proposed. A consequence of this approach, where patients can be in the L-SAF for very varying amounts of time is that adverse event (and adverse reaction) rates will be presented based on person-years at risk, and not simply based on the total number of patients who are ever in the L-SAF.
- The Lamzede Effectiveness analysis set (L-FAS) will contain patients included in the Lamzede Safety analysis set at the times when they have been taking Lamzede, and for 12 months thereafter excluding patients without any valid measurement and those with major protocol deviations affecting the effectiveness evaluations. The consequence of this is that

Clinical Protocol Number: CLI-LMZYMAA1-12	
Clinical Protocol Version Number: 8.0	Date: 01 February 2019

"baseline" will be clearly defined for each patient – namely the time they started to take Lamzede, not necessarily the time they enter the study. So a patient can be excluded from the L-FAS for some of their time in the study, and then join the L-FAS. In such cases, their "baseline" would be the time when they started.

- The No-Lamzede Safety analysis set (NL-SAF) will include patients only for the time when they are not (and have not within 1 month) been taking Lamzede.

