- The No-Lamzede Effectiveness analysis set (NL-FAS) will include patients only for the time when they are not (and have not within the 12 months) been taking Lamzede.

Exact definitions of major Protocol deviations will be discussed by the clinical team case by case during the Data Review Meeting and described in the Data Review Document.

A summary table reporting the reason for exclusion from analysis sets will be presented.

The primary objective of the study (i.e. to assess the long-term effectiveness and safety of treatment with Lamzede) will be based on the Lamzede Safety analysis set (L-SAF) for safety variables and on the Lamzede Effectiveness analysis set (L-FAS) for effectiveness and other variables.

The secondary objectives of the study will be based on the No-Lamzede Safety analysis set (NL-SAF) for safety variables and on the No-Lamzede Effectiveness analysis set (NL-FAS) for effectiveness and other variables.

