9.7.4 Effectiveness Variables

Effectiveness will be assessed by:

• Oligosaccharides in serum (µmol/L)

Clinical Protocol Number: CLI-LMZYMAA1-12

Clinical Protocol Version Number: 8.0

- 3MSCT (step/min)
- 6MWT (m)
- 2MWT (m)
- FVC (as litre and as percentage of predicted)
- EQ-5D-5L
- Zarit Burden Interview
- CHAQ
- Rate and length of infections (requiring or not antibiotic)
- Serum IgG, IgA and IgM
- Rate of psychotic events
- Behavior Checklists: CBCL prescholar (1.5-5) and scholar (6-18); Adult Behavior Checklist (19-59)/ASR, Older Adult Behavior Checklist (60-and above).

All effectiveness variables will be summarised by means of descriptive statistics or frequency distribution, as appropriate. All variables (actual values and change from baseline, if applicable) will be presented by time point. In addition, mean and individual profiles by time will be produced.

Since alpha-mannosidosis presents as a multi-systemic disease, characterized by many clinical manifestations, a Global Treatment Response (GTR) will be evaluated by aggregating single endpoints in 3 disease relevant domains: pharmacodynamics (reduction of serum oligosaccharides), functional (3MSCT, 6MWT and FVC % of predicted) and quality of life (improvement in CHAQ Disability Index and VAS pain). Patients will be considered responders in one domain if the Minimal Clinical Important Difference (MCID) established for each endpoint from proxy diseases will exceeded in at least one endpoint of the domain; GTR will be reached by patients responding in at least 2 domains.

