At the time of planning this registry, adopted MCID are: oligosaccharides below 4 umol/L, increase of 7 steps/minute for 3MSCT (proxy: MPS IV A), increase of 30 meters for 6MWT (proxy: Pompe disease), increase of 10% for FVC (proxy: Pompe disease), decrease of 0.13 for CHAQ DI (proxy: Juvenile Arthritis) and of 8.2% for CHAQ pain (as in paediatric rheumatology). However, taking into account the length of this registry and the disease characteristics, if new scientific factors (i.e. knowledge about alpha-mannosidosis, clinical guidance) emerge the criteria used to establish the GTR may be reviewed and additional criteria may be added (like, but not limited to, EQ-5D-5L and serum IgG). The Global Treatment Response rate after 3 years of Lamzede treatment in naïve patients able to perform the functional tests will be evaluated. The proportion of responders and the corresponding exact (Clopper-Pearson) two-sided 95% confidence interval (CI) will be presented.

Effects of baseline characteristics will be evaluated by means of regression/logistic models including:

- age subgroup (<18 years, \geq 18 years),
- gender (male, female),
- genotype by subcellular localization of the protein (Genotype Group 1, Genotype Group 2, Genotype Group 3, as defined by Borgwardt et all., 2015)
- baseline residual enzymatic activity (<10 nmol/h/mg, 10 to <15 nmol/h/mg, \geq 15 nmol/h/mg)
- baseline CHAQ Disability Index (0|-|1, 1-|2, 2-|3)

as covariates.

Clinical Protocol Number: CLI-LMZYMAA1-12	
Clinical Protocol Version Number: 8.0	Date: 01 February 2019

Comparison with control group will be done descriptively, provided that a minimum number of nontreated patients with adequate data will be enrolled. If data will allow, Global Treatment Response after 3 year will be analysed comparing the two groups using propensity score (PS) analysis. The PS will be calculated as the predicted probability of Lamzede-treated vs non-treated patients from a logistic regression. This score represents the "propensity" for an observation to be in a treatment group or the other. The logistic regression model will include the following confounding factors as explanatory variables:

- age subgroup (<18 years, \geq 18 years),
- gender (male, female),
- genotype by subcellular localization of the protein (Genotype Group 1, Genotype Group 2, Genotype Group 3, as defined by Borgwardt et all., 2015)
- baseline residual enzymatic activity (<10 nmol/h/mg, 10 to <15 nmol/h/mg, \geq 15 nmol/h/mg)

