9.7.7 Missing Data

Patients with missing values will not be excluded from the analysis, but their data will not be replaced. Further details on dealing with missing data, along with the handling of possible outliers, will be described in the SAP. Other critical missing data, if any, will be discussed during the Data Review Meeting. Decisions will be fully documented in the Data Review Document.

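### The denominator of the primary 3-year GTR rate is not anchored at Lamzede start, so early stoppers and deaths can leave the rate instead of counting against it

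*Protocol*

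**What the plan says.** Section 9.7.4 defines the estimate: "The Global Treatment Response rate after 3 years of Lamzede treatment in naïve patients able to perform the functional tests will be evaluated". A patient responds in a domain by exceeding the threshold on any one of its endpoints, and "GTR will be reached by patients responding in at least 2 domains".

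Section 9.7.1 assigns effectiveness under the primary objective to L-FAS. That set contains Lamzede-treated patients "at the times when they have been taking Lamzede, and for 12 months thereafter excluding patients without any valid measurement", and it also drops those with major deviations that affect effectiveness. Time off Lamzede for more than 12 months belongs to the No-Lamzede Effectiveness set (NL-FAS). On deviations, section 9.7.1 says "Exact definitions of major Protocol deviations will be discussed by the clinical team case by case during the Data Review Meeting". Section 9.6 places that meeting once the data have been gathered and cleaned: "a review meeting will be held to determine the occurrence of any protocol violation and to define the patient populations for the analysis".

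Table 1, footnote 5 (section 9.2.6), has the physical examination record "the ability to perform the endurance test at the study visit". On missing data, section 9.7.7 says "Patients with missing values will not be excluded from the analysis, but their data will not be replaced" and leaves further detail to the SAP.

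Section 9.1 lets patients stop Lamzede at any time. Section 9.5 takes 70 treated patients and treats a lower 95% limit above 45% as clinically relevant.

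**The concern.** The clinical question is what share of naïve patients who start Lamzede are responders 3 years later. That question fixes its denominator at the first infusion. The plan instead takes whoever is inside L-FAS at year 3, and membership at that time depends on what happened after the start.

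Two further features leave the denominator open. The text does not say when a patient must be able to perform the functional tests. The deviation exclusions have no criteria until the data are complete and, in an unblinded registry, outcomes can be known by then.

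If those who leave are mainly patients who did poorly, the reported proportion is too high. What is at stake is whether the interval clears the protocol's own 45% mark. A survivor who stopped early may also reappear in NL-FAS, the natural source of the untreated side of the optional propensity-score comparison in section 9.7.4.

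**Working it through.** **1. What the set rules do at year 3 (month 36).** L-FAS membership ends 12 months after the last treated time.
- Stop at month 18: 18 + 12 = month 30. The patient has no L-FAS time at month 36, and later data fall in NL-FAS.
- Stop at month 24: 24 + 12 = month 36. This is the break-even point, give or take the visit window.
- Stop at month 30: L-FAS runs to month 42, so the patient is still in the set at year 3, but has not had 3 years of treatment as section 9.7.4 words it.
- Death before month 36: no data at year 3, and no rule scores the patient.

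**2. The protocol's own figures.** Exact limits for x responders among n are: lower = 0.025 quantile of Beta(x, n − x + 1); upper = 0.975 quantile of Beta(x + 1, n − x). With n = 70 and x = 42 this gives 0.476 to 0.715 (width 0.239). With x = 56 it gives 0.687 to 0.886 (width 0.199). All five rows of the section 9.5 table reproduce, so the arithmetic there is sound. The issue is who makes up n.

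**3. Effect of the denominator.** Assumptions: 70 naïve starters (section 9.5's number, which it calls treated patients); a response rate of about 0.70 among those remaining; a lost share of 10% to 30%, because the documents give no rate.

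| Lost | Lost patients dropped (95% CI) | Counted as non-responders (95% CI) | All counted as responders |
|---|---|---|---|
| 7 (10%) | 44/63 = 0.698 (0.570–0.808) | 44/70 = 0.629 (0.505–0.741) | 51/70 = 0.729 |
| 14 (20%) | 39/56 = 0.696 (0.559–0.812) | 39/70 = 0.557 (0.433–0.676) | 53/70 = 0.757 |
| 21 (30%) | 34/49 = 0.694 (0.546–0.817) | 34/70 = 0.486 (0.364–0.608) | 55/70 = 0.786 |

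**4. The 45% mark.** With n = 70, 41 responders give a lower limit of 0.462 and 40 give 0.4475, so 41 are needed. With those lost counted as non-responders, the mark is missed once 3 of 70 (4%), 13 of 70 (19%) or 20 of 70 (29%) are lost, at rates among the remainder of 0.60, 0.70 and 0.80.

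**5. Sensitivity to who is lost.** In the 20% row, dropping the 14 overstates the rate only if 9 or fewer of them would count as responders: (39 + 9)/70 = 0.686, against (39 + 10)/70 = 0.700. Two responders among the 14 would restore 41/70. The crossing of 45% therefore rests on counting stopping and death as non-response.

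**The case against.** A reader might infer four stronger things that the text does not support.

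- *That the rate is conditioned on being able at year 3.* A baseline reading is the more natural one. The abstract's data-analysis paragraph pairs ability with being naïve and attaches the 3 years to the response. Section 9.3.1 lists ability among baseline items, and section 9.3.3 links inability to age under 4. Recording it at later visits does not make it a denominator rule. What stands is that no time point is written.
- *That losing ambulation removes a patient.* FVC, serum oligosaccharides and the parent-completed CHAQ need no walking, and one endpoint per domain is enough.
- *That missing tests inflate the rate.* Section 9.7.7 keeps patients with missing values. If an undone test counts as not met, the rate falls.
- *That exclusions are driven by outcomes.* The timing and lack of blinding allow this, but nothing says it happens, and a table of reasons for exclusion is promised.

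The 12-month tail also protects those who stop after about year 2. Section 9.7.2 promises a description of every switch, and section 7.1 places progression over decades, which gives no basis for a particular 3-year loss.

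The remaining objection is that scoring rules belong in the SAP. That is fair for undone tests, but not for the analysis set, which the protocol itself fixes. Section 9.7.5 even states the matching safety rule: withdrawn patients stay in and count as event-free. Section 9.7.7 concerns missing values and does not bring back patients outside L-FAS.

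**Conclusion.** The point holds as a defect in how the denominator is fixed. As written, naïve starters who stop before about year 2, or who die before year 3, fall outside the 3-year rate, and early stoppers who survive pass into NL-FAS. The undated ability condition and the late deviation criteria add to the uncertainty about who is counted.

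The rate *can* be overstated. That it *is* inflated does not follow, because the size and strictly the sign depend on who is lost. With an assumed 20% loss from 70 starters and about 0.70 among the rest, the gap is 0.696 − 0.557 = 0.139, and the lower limit moves from 0.559 to 0.433, across the 45% mark. At 10% loss the gap is about 0.07 and the mark is still cleared (0.505). These figures rest on the assumed loss, on 70 being naïve starters, and on counting those lost as non-responders.

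**What to change.** In section 9.7.4, and in the abstract to match:

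- Define the denominator as all naïve patients able to perform the functional tests at their pre-treatment baseline whose Lamzede start was at least 3 years (plus the visit window) before the data cut-off, irrespective of later ability or persistence.
- Count death and permanent discontinuation before year 3 as non-response in the main rate, and show the on-treatment L-FAS rate alongside.
- Score patients who lose ambulation on the endpoints still measurable (FVC, oligosaccharides, CHAQ), and give best- and worst-case bounds for tests not done.
- Use the exclusion for major deviations only as a sensitivity analysis, or fix its criteria before outcomes are reviewed.
- State how early stoppers enter the propensity-score comparison.

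The cost is wording and slightly more analysis. Lamzede exposure, ability and deaths are already to be collected. The reported rate may be lower.

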Lamzede (velmanase alfa, henceforth referred to as Lamzede) is a recombinant human lysosomal alpha-mannosidase product, developed as an intravenous enzyme replacement therapy (ERT) for the treatment of alpha-mannosidosis. The safety and efficacy of Lamzede in adults and children (\geq 6 years old) has been evaluated in 33 patients (20 males and 13 females; 19 children [paediatric group, aged younger than 18 years] and 14 adults; median age 17.1 years, range 6.0-35 years) in five clinical studies (three exploratory Phase I to IIb studies, one Phase III pivotal study and one Phase III long-term efficacy and safety evaluation (rhLAMAN-10) in all patients previously enrolled in clinical trials with under-treatment data for up to 48 months).

The rhLAMAN-10 open-label, uncontrolled, phase III study encompassed an integrated database created by pooling cumulative databases from all studies with Lamzede together with an additional long-term assessment endpoint. Statistically significant improvements were detected in serum oligosaccharide levels, 3-minute stair climb test (3MSCT) and pulmonary function over time, up to the last observation. The effects of Lamzede were more evident in patients younger than 18 years. Descriptive evidence of improvement was also documented in several additional clinical endpoints, including serum immunoglobulin G (IgG), Bruininks-Oseretsky Test Of Motor Proficiency–2nd Edition (BOT-2) subdomains and Childhood Health Assessment Questionnaire (CHAQ) Disability Index, CHAQ visual analogue scale (VAS) Pain, European Quality of Life Five Dimension Five Level Scale (EQ-5D-5L) Health Index. A progressive improvement from baseline was also evident in the 6-minute walk test (6MWT). For further details, refer to the Lamzede Summary of Product Characteristics (SmPC).

A multi-domain post-hoc responder analyses was conducted across the pharmacodynamics (serum oligosaccharide response only), functional (3MSCT, 6MWT and Forced Vital Capacity (FVC) % predicted) and quality of life (CHAQ disability index and CHAQ VAS pain) domains.

A clinically significant response for each domain was claimed when at least one parameter of the domain improved beyond the proposed MCID.

In the overall responder analysis, a patient was qualified as responder to treatment if response criteria was reached in at least two domains. The alpha-mannosidosis Response Model generated as part of this approach is depicted in Figure 1.

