Figure 1 Alpha-Mannosidosis Treatment Response Models Treatment Response Model

Chiesi	
Clinical Protocol Number: CLI-LMZYMAA1-12	
Clinical Protocol Version Number: 8.0	Date: 01 February 2019

Source: Provided by Chiesi

Based on the MCID-based Treatment Response Model, the Global Response to Treatment (GRT) of rhLAMAN-05 shows a discernible treatment difference between the two groups, with a clinical response in at least two domains at 12 months observed in 87% of patients treated with velmanase alfa compared to 30% in placebo. Moreover, 13% treated patients but none of the placebo patients reported a clinically-significant response in all three domains (Figure 3).

In the single-arm, integrated analysis from rhLAMAN-10 study, a remarkably similar proportion of 79% of patients showed a significant response in at least two domains at 12 months, 24% in all three. The proportion increases at Last Observation with a clinically meaningful response in at least two domains achieved in 88% patients (100% of paediatric patients and 71% of adult patients) and in at least three domains in 45% patients (53% of paediatric patients and 36% of adult patients) (Figure 2). The proposed domains are aligned with the representation of (a) the clinical burden, (b) the endpoints hierarchy defined with the CHMP, (c) the measurements of the benefit perceived by the patients (health-related QoL).

Figure 2 Global Response to Treatment in rhLAMAN-10 Study Integrated Analysis

Collesi	
Clinical Protocol Number: CLI-LMZYMAA1-12	
Clinical Protocol Version Number: 8.0	Date: 01 February 2019

The most common adverse reactions observed during treatment with Lamzede were weight increase (18%), infusion-related reactions (9%), diarrhoea (12%), headache (9%), arthralgia (9%), increased appetite (6%) and pain in the extremities (6%). A total of two serious adverse reactions (loss of consciousness in one patient and acute renal failure in one patient) considered possibly related to study treatment were observed; both cases recovered without sequelae. For further safety information, refer to the Lamzede SmPC.

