9.2 Setting

9.2.1 Subject Recruitment

The eligible patient population for this Registry includes any patient in the EU suffering from alpha-mannosidosis who is willing to participate, and who meets the inclusion criteria (see below) for this Registry. The recruitment period will be indefinite.

About 30 patients are foreseen as coming from previous Lamzede clinical trials. Each patient will be followed-up for 15 years.

Based on the current unmet medical need, patients can start Lamzede treatment independently from the Registry set up.

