9.5 Study Size

All patients with alpha-mannosidosis who is willing to participate will be included in the Registry. The size of the registry study is not based on the power to demonstrate a formal statistical hypothesis. However, some scenarios are presented in the table below, considering different proportions of GTR in naïve patients able to perform the functional tests after 3 years of treatment. The proportion of responders, the corresponding expected 95% confidence interval and the confidence width are shown below, assuming at least 70 treated patients will be enrolled.

In this case, it is expected that an exact (Clopper-Pearson) two-sided 95% confidence interval (CI) might be provided with a width ranging from 0.239 (worst case) to 0.199 (best case) assuming GTR of 0.60 or more. Of note, in all scenarios the lower limit of 95% CI is always greater than 45% which is considered a clinical relevant result.

Expected Proportion	95% CI Lower Limit	95% CI Upper Limit	95% CI Actual width
0.60	0.476	0.715	0.239
0.65	0.527	0.760	0.234
0.70	0.579	0.804	0.225
0.75	0.632	0.846	0.214
0.80	0.687	0.886	0.199

Clinical Protocol Number: CLI-LMZYMAA1-12

9.6 Data Management

An eCRF will be filled-in by the investigator and/or his/her representative designee.

Front-end edit checks will run at the time of data collection and back-end edit checks will be used by the Data Manager to check for discrepancies and to ensure consistency and completeness of the data. Questionnaires will be collected on paper and data will be entered in the database by the allocated Contract Research Organisation (CRO).

Medical history, AEs and concomitant procedures will be coded using the Medical Dictionary for Regulatory Activities (MedDRA) dictionary; medications will be coded using the World Health Organization Drug dictionary and Anatomical Therapeutic Chemical classification.

The dictionary version to be use will be the most current version at the time the data collection starts. Considering the long duration of the study, the versions could be updated during the trial by re-coding all terms already entered in database according to the new dictionary version. Re-coded terms will be reviewed by Chiesi for approval.

The detailed process and the coding tools will be specified in the Data Management Plan once the CRO will be selected.

External data (i.e. laboratory data) will be processed centrally^a and results will be sent electronically to the designated CRO.

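### The covariate model for Global Treatment Response has 8 coefficients for about 5 to 28 expected non-responders, and its age-group effect has no finite maximum-likelihood estimate if no child fails to respond

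*Protocol*

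**What the plan says.** Section 9.7.4 gives the effectiveness estimand: "The Global Treatment Response rate after 3 years of Lamzede treatment in naïve patients able to perform the functional tests will be evaluated". It then says "Effects of baseline characteristics will be evaluated by means of regression/logistic models including" five factors as covariates, and fixes the classes:

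- age in two classes, cut at 18 years;
- gender in two;
- genotype group in three;
- residual enzymatic activity in three;
- baseline CHAQ Disability Index in three.

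No condition on the amount of data is attached to this model.

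Section 9.5 plans by precision, "assuming at least 70 treated patients will be enrolled", and gives an interval "width ranging from 0.239 (worst case) to 0.199 (best case) assuming GTR of 0.60 or more". Section 9.2.1 adds: "About 30 patients are foreseen as coming from previous Lamzede clinical trials".

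Section 7.1 reports the earlier integrated study, which had "19 children [paediatric group, aged younger than 18 years] and 14 adults". At last observation, response in at least two domains was "achieved in 88% patients (100% of paediatric patients and 71% of adult patients").

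**The concern.** A logistic model is limited by the smaller outcome group, which here is the non-responders. Eight class contrasts spread over a handful of non-responders leave some classes with none or nearly none. The likelihood then keeps rising as a coefficient goes to infinity (separation). Software reports a huge odds ratio with a meaningless standard error, or fails to converge.

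This model is the planned analysis of which baseline features go with response. If it breaks down, a replacement method has to be chosen after the results are known. The protocol's own earlier data show the pattern that causes this, since all non-responders appear to have been adults.

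**Working it through.** **The plan's own figure.** With n = 70 and x = 70 × p, the Clopper-Pearson limits reproduce all five rows of the table in section 9.5 to three decimals, from 0.476–0.715 at p = 0.60 to 0.687–0.886 at p = 0.80. So that table counts all 70 treated patients.

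**Model size.** Sum of (levels − 1): age 1 + gender 1 + genotype 2 + enzymatic activity 2 + CHAQ Disability Index 2 = 8 coefficients, or 9 with the intercept.

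**Naive patients.** If the roughly 30 former trial patients (section 9.2.1) are among the 70 (section 9.5), 70 − 30 = 40 are naive. The protocol does not say that they are, so both 40 and 70 are shown.

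**Non-responders** = n × (1 − GTR), then divided by 8. GTR 0.60 and 0.80 are the ends of the planning table; 0.88 is the earlier study.

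| n naive | GTR | Non-responders | Per coefficient |
|---|---|---|---|
| 40 | 0.60 | 16.0 | 2.0 |
| 40 | 0.80 | 8.0 | 1.0 |
| 40 | 0.88 | 4.8 | 0.6 |
| 70 | 0.60 | 28.0 | 3.5 |
| 70 | 0.80 | 14.0 | 1.75 |
| 70 | 0.88 | 8.4 | 1.05 |

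**Earlier study.** The percentages in section 7.1 fit 19/19 children (100%) and 10/14 adults (71.4%), together 29/33 = 87.9%. The exact 95% interval for 19/19 is 82.4% to 100%.

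**Age effect when no child fails.** Scale the 19:14 split to n = 40: about 23 children, all responding, and 17 adults, 12 responding. In a maximum-likelihood fit with age group alone, the log odds ratio is 5.7, 10.7, 20.7 and 30.7 after 5, 10, 20 and 30 iterations. Its standard error goes from 3.4 to about 900,000. There is no finite maximum.

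**How often the 8-coefficient model has no finite fit.** 500 simulated samples per cell, with separation tested by linear programming. Assumptions: 19/33 children, 20/33 males, three-level factors split equally and unrelated to response.

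| Response, children / adults | n = 40 | n = 70 |
|---|---|---|
| 100% / 71% | 100% | 100% |
| 95% / 71% | 74% | 26% |
| 90% / 71% | 55% | 12% |
| 80% / 80% | 41% | 6% |
| 60% / 60% | 3% | 0% |

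Repeat runs move these by a few points; the 80% row ranges over 41–44% and 6–9%. The 95% and 90% paediatric rates are illustrations and do not come from the protocol.

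**Effect of continuous terms.** Entering age, enzymatic activity and CHAQ Disability Index as continuous gives 1 + 1 + 2 + 1 + 1 = 6 coefficients. In the 100% / 71% case, samples without a finite fit fall from 100% to about 52–54% at n = 40 and 14–21% at n = 70, depending on the assumed age spread. Penalised estimation gives finite estimates in the rest.

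**The case against.** **The estimator is not named.** Section 9.7 leaves detailed methodology to the SAP, so a penalised or exact fit would be compatible with the protocol. That stands for the estimator. It does not cover the covariate list and the class boundaries, which section 9.7.4 itself fixes.

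**The 100% paediatric response is not a registry assumption.** It comes from a post-hoc analysis at last observation in 19 children, not from a 3-year rate in routine care. This stands: separation on age is certain only if no child fails to respond. The figure also belongs with the low end of the non-responder range. Sixteen non-responders at n = 40 with all children responding would require 16 of about 17 adults (94%) to fail.

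**Forty naive patients is inferred and 70 is a minimum.** Both are true, and enrolment is open-ended. Even so, 70 naive patients at the lowest planning rate give only 3.5 non-responders per coefficient. In the other direction, naive patients who cannot do the functional tests fall outside the estimate. Missing values are not replaced (section 9.7.7), so a patient lacking one covariate drops out of an ordinary joint fit.

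**The wording may not mean one joint logistic model.** Models are mentioned in the plural, and some may have continuous outcomes, where separation does not arise. Listing all five factors as covariates still reads most naturally as a joint model.

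**The propensity score.** A reader might infer that the same numbers undermine the propensity model, for which "The logistic regression model will include the following confounding factors as explanatory variables", with the same list. The documents do not support that. Its outcome is treatment status, so its limiting count is the number of untreated patients, which the protocol does not give. Paediatric response has no bearing on it. The analysis runs only if the data allow, and similarity of the score distributions is already to be evaluated.

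**Conclusion.** The response model is too large for the expected number of non-responders: 0.6 to 3.5 per coefficient over every combination of 40 or 70 naive patients with GTR from 0.60 to 0.88. If the earlier paediatric result recurs, its age-group effect cannot be estimated by maximum likelihood at all. At the protocol's planning rates, failure to obtain a finite fit is a substantial risk only for about 40 naive patients with response near 80%. It is uncommon with 70 patients, and rare at 60% response, although estimates remain imprecise there.

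A reader might go further and infer that the covariate analysis is bound to fail or that the main effectiveness result is compromised. Neither follows. The primary GTR proportion and its Clopper-Pearson interval do not use this model, and the registry tests no formal hypothesis. An infinite age coefficient also does not by itself make the other coefficients infinite.

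The simulated percentages rest on equal splits of the three-level factors and on no effect of those factors on response; unequal splits would change them. This is an inexpensive improvement to a supportive analysis.

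**What to change.** In section 9.7.4, for the GTR covariate model:

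- fit by Firth-penalised logistic regression with profile-likelihood confidence intervals;
- enter age, residual enzymatic activity and CHAQ Disability Index as continuous terms, giving 6 coefficients instead of 8;
- report univariable results for each factor alongside;
- label the joint model exploratory.

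Continuous terms alone are not enough. Six coefficients still leave 4.8/6 = 0.8 to 28/6 = 4.7 non-responders each, so the penalised fit is the essential part.

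The cost is a few lines of wording and standard software, with no extra data. The price is slight shrinkage of the estimates, and odds ratios per unit rather than per class for three of the factors. No change to the propensity-score text is asked for here.
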